7.1.2. Recording and Reporting Adverse Events

For adverse event recording, the study period is defined for each patient as the time period from signature of the informed consent form for this study through the follow-up visit (approximately 7.5 months after the final dose of study drug). Adverse events will be collected at each visit via adverse event inquiry.

All adverse events that occur during the defined study period must be recorded on the source documentation and transcribed onto the CRF, regardless of the severity of the event or judged relationship to the study drug. For serious adverse events, the serious adverse event form must also be completed and the serious adverse event must be reported immediately (see Section [7.1.5.3.1](#)). The investigator does not need to actively monitor patients for adverse events once the study has ended. Serious adverse events occurring to a patient after the defined study period should be reported to the sponsor if the investigator becomes aware of them, following the procedures described in Section [7.1.5.3.1](#).

At each contact with the patient, the investigator or designee must question the patient about adverse events by asking an open-ended question such as, "Have you had any unusual symptoms or medical problems since the last visit? If yes, please describe." All reported or observed signs and symptoms will be recorded individually, except when considered manifestations of a medical condition or disease state. A precise diagnosis will be recorded whenever possible. When such a diagnosis is made, all related signs, symptoms, and any test findings will be recorded collectively as a single diagnosis on the CRF and, if it is a serious adverse event, also on the serious adverse event form.

The clinical course of each adverse event will be monitored at suitable intervals until it resolves, stabilizes, or returns to baseline, or until the patient is referred for continued care to a another health care professional, or until a determination of a cause unrelated to the study drug or study procedure is made.

The onset and end dates, duration (in case of adverse event duration of less than 24 hours), action taken regarding study drug, treatment administered, and outcome for each adverse event must be recorded on the source documentation and transcribed onto the CRF.

The relationship of each adverse event to study drug and study procedures, and the severity and seriousness of each adverse event, as judged by the investigator, must be recorded as described below.

7.1.3. Severity of an Adverse Event

The severity of each adverse event must be recorded as 1 of the choices on the following scale:

Mild: No limitation of usual activities

Moderate: Some limitation of usual activities

Severe: Inability to carry out usual activities

7.1.4. Relationship of an Adverse Event to the Study Drug

The relationship of an adverse event to the study drug is characterized as follows:

Term	Definition	Clarification
No reasonable possibility (not related)	This category applies to adverse events that, after careful consideration, are clearly due to extraneous causes (disease, environment, etc) or to adverse events that, after careful medical consideration at the time they are evaluated, are judged to be unrelated to the study drug.	The relationship of an adverse event may be considered “no reasonable possibility” if it is clearly due to extraneous causes or if at least 2 of the following apply: 
 • It does not follow a reasonable temporal sequence from the administration of the study drug. • It could readily have been produced by the patient’s clinical state, environmental, or toxic factors, or other modes of therapy administered to the patient. • It does not follow a known pattern of response to the study drug. • It does not reappear or worsen when the study drug is re-administered.
Reasonable possibility (related)	This category applies to adverse events for which, after careful medical consideration at the time they are evaluated, a connection with the study drug administration cannot be ruled out with certainty.	The relationship of an adverse event may be considered “reasonable possibility” if at least 2 of the following apply: 
 • It follows a reasonable temporal sequence from administration of the study drug. • It cannot be reasonably explained by the known characteristics of the patient’s clinical state, environmental or toxic factors or other modes of therapy administered to the patient. • It disappears or decreases on cessation or reduction in dose. There are important exceptions when an adverse event does not disappear upon discontinuation of the study drug, yet a drug relationship clearly exists. • It follows a known pattern of response to the study drug.

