5. TREATMENT OF PATIENTS

5.1. Drugs Administered During the Study

Patients rolling over from the pivotal efficacy studies who were randomized to the active treatment groups and will continue receiving study drug in the current study will continue receiving the same treatment (ie, monthly TEV-48125 at 225 mg or quarterly TEV-48125 at 675 mg) throughout this long-term safety, tolerability, and efficacy study. Patients rolling over from the pivotal efficacy studies who received placebo and will continue receiving study drug in the current study and patients not rolling over will be randomly assigned in a 1:1 ratio using IRT as follows:

- Patients with CM will receive sc TEV-48125 at 675 mg (loading dose) followed by 11 monthly sc doses of TEV-48125 at 225 mg or sc TEV-48125 at 675 mg once every 3 months for 12 months for a total of 4 doses.
- Patients with EM will receive monthly sc TEV-48125 at 225 mg for 12 months or sc TEV-48125 at 675 mg once every 3 months for 12 months for a total of 4 doses

Study drug will be administered by qualified study personnel as sc injections approximately every 4 weeks (28 days). The 4-week period will be determined relative to the planned dosing day provided the patient returns to the study center within the tolerance window (± 5 days). If the patient returns to the study center more than 5 days late, then the 4-week period will be determined from the actual dosing day rather than the planned dosing day.

In order to maintain the study blind, all patients will receive 3 injections at visits 2, 5, 8, and 11 and 1 injection at all other visits as detailed in [Table 4](#).

Table 4: Study Drug Administration by Treatment Group and Visit

Treatment group in this study	Visit 2	Visits 5, 8, and 11	Visits 3, 4, 6, 7, 9, 10, 12, and 13
Loading dose of TEV-48125 at 675 mg followed by monthly TEV-48125 at 225 mg	3 active injections (225 mg/1.5 mL)	1 active injection (225 mg/1.5 mL) and two 1.5-mL placebo injections	1 active injection (225 mg/1.5 mL)
Monthly TEV-48125 at 225 mg	1 active injection (225 mg/1.5 mL) and two 1.5-mL placebo injections	1 active injection (225 mg/1.5 mL) and two 1.5-mL placebo injections	1 active injection (225 mg/1.5 mL)
Quarterly TEV-48125 at 675 mg	3 active injections (225 mg/1.5 mL)	3 active injections (225 mg/1.5 mL)	one 1.5-mL placebo injection

Individual visit kits containing 1 prefilled syringe with a staked 27 G ½” needle will be provided.

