7.1.8. Overdose of Study Drug

Any dose of study drug (whether the investigational product or placebo), whether taken intentionally or unintentionally, in excess of that prescribed must be immediately reported to the sponsor. When the identification of the study drug must be known, the investigator must follow the procedures outlined in Section 3.8.

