7.3. Adverse Events

All adverse events will be coded using the MedDRA version 18.1.

For adverse event recording, the study period is defined for each patient as the time period from signature of the informed consent form for this study through the follow-up visit (approximately 7.5 months after the final dose of study drug). Adverse events will be collected at each visit via adverse event inquiry. The onset and end dates, duration (in case of adverse event duration of less than 24 hours), action taken regarding study drug, treatment administered, and outcome for each adverse event must be recorded on the source documentation and transcribed onto the CRF.

The following are considered protocol-defined adverse events to be sent to the sponsor's Global Patient Safety and Pharmacovigilance Department for evaluation: ophthalmic adverse events of at least moderate severity, events of possible drug-induced liver injury (aspartate aminotransferase or alanine aminotransferase $\geq 3 \times$ the upper limit of the normal range [ULN], total bilirubin $\geq 2 \times$ the ULN or international normalized ratio >1.5), Hy's Law events, or events of suspected anaphylaxis and severe hypersensitivity reactions. Severe hypersensitivity reactions will be monitored using the diagnostic criteria for anaphylaxis as outlined by the 2006 Joint National Institute of Allergy and Infectious Disease/Food Allergy and Anaphylaxis Network Second Symposium on Anaphylaxis ([Sampson et al 2006](#)). In the event of suspected anaphylaxis, vital signs, including oxygen saturation and respiration rate, will be measured.

Summaries by treatment group and overall will be presented for treatment-emergent adverse events (overall and by severity), treatment-emergent adverse events determined by the investigator to be treatment-related adverse events (overall and by severity), serious adverse events, protocol-defined adverse events, adverse events causing discontinuation from the study, non-serious treatment-emergent adverse events, and prior to treatment adverse events. Additionally the injection site reactions recorded as adverse events will be summarized by treatment group separately.

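### The causality criteria in protocol 7.1.4 count non-recurrence on re-administration against drug causation without requiring active drug, so some treatment-related events may be understated in the quarterly arm

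*Protocol*

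**What the plan says.** Protocol 7.1.4 offers two categories. Each has a general definition and a list of four clarifying items, and each may be chosen "if at least 2 of the following apply". Three items appear in both lists with opposite sign: timing, alternative explanation and known pattern. The fourth differs. For *not related* it is "It does not reappear or worsen when the study drug is re-administered". For *related* it is "It disappears or decreases on cessation or reduction in dose". The general definition of *related* covers events for which "a connection with the study drug administration cannot be ruled out with certainty".

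No item says what to do when the repeated injection may have been placebo. The term study drug is not tied to active product throughout: section 7.1.8 speaks of "Any dose of study drug (whether the investigational product or placebo".

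Protocol Table 4 (section 5.1, repeated as SAP Table 5) gives the quarterly arm active drug at visits 2, 5, 8 and 11, and "one 1.5-mL placebo injection" at visits 3, 4, 6, 7, 9, 10, 12 and 13. Both monthly regimens include at least one active injection at every dosing visit. Investigators are blinded (protocol 3.7).

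SAP 7.3 plans a summary by treatment group of "treatment-emergent adverse events determined by the investigator to be treatment-related adverse events", and protocol 9.7.2 plans the equivalent.

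**The concern.** An event triggered by an active quarterly dose that stays away at the next visit has not been rechallenged. The patient received placebo, so the observation is closer to a dechallenge, which counts toward *related*. The blinded investigator cannot tell this and may tick the non-recurrence item, which counts toward *not related*. The same observation can thus push the judgement the wrong way, and only in the arm with placebo-only visits.

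The study has no untreated comparator (protocol 3.9 calls it uncontrolled), so investigator attribution carries some weight when the related-event table is read by arm. Protocol 3.8.2 also ties the definition of a suspected unexpected serious adverse reaction to the *related* category of 7.1.4. The exposure is greatest for an unrecognised reaction, which already scores one item against the drug because it fits no known pattern.

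**Working it through.** **Schedule (Table 4).** The quarterly arm has active drug at visits 2, 5, 8 and 11. That is 4 doses, as section 5.1 states. The visits that follow are 3, 6, 9 and 12, all placebo-only: 4 of 4. Over the 11 steps between consecutive dosing visits (2→3 to 12→13), the next injection is placebo-only in 8 of 11 in the quarterly arm and 0 of 11 in the monthly arms.

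**Scoring rule.** Let

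- s = how many of the three mirrored facts favour the drug (timing fits, no other cause, known pattern), from 0 to 3;
- N = 1 if non-recurrence on re-administration is scored, otherwise 0;
- D = 1 if the event subsided on cessation or dose reduction, otherwise 0.

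Then the *not related* score is (3 − s) + N, and the *related* score is s + D. A category is available at a score of 2 or more.

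| s | Fact patterns | *Not related* available? | *Related* available? |
|---|---|---|---|
| 3 | 1 | never (at most 1) | always |
| 2 | 3 | only if N = 1 | always |
| 1 | 3 | always | only if D = 1 |
| 0 | 1 | always | never (at most 1) |

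**What N changes.** Counting both values of D, *not related* is available in (3 + 1) × 2 = 8 of 16 patterns when N = 0, and in (3 + 3 + 1) × 2 = 14 of 16 when N = 1. The 6 patterns gained are the row s = 2, and all 6 also meet the *related* list.

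**Key example.** Timing fits, there is no other cause, and the pattern is not known, so s = 2. If the event recurs on active drug, N = 0 and the *not related* score is 1: unavailable. If it does not recur after a placebo injection and this is scored, N = 1 and the score is 2: available.

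**Typical injection-site reaction.** It is timely, has no other cause and follows a known pattern, so s = 3. The *not related* score is at most 1, and the item cannot change the call.

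**Overlap of the two lists.** Both are met when s = 2 and N = 1 (3 × 2 = 6 patterns) or when s = 1 and D = 1 (3 × 2 = 6 patterns), so 12 of 32. If D is taken as unobservable (D = 0), the overlap is 3 of 16.

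**Drug still present at the placebo visit.** With the half-life of about 45 days in protocol 3.11, the fraction left after 28 days is 2^(−28/45) = 0.65. Over the 27 to 50 days reported in protocol 1.3.2.1 it runs from 2^(−28/27) = 0.49 to 2^(−28/50) = 0.68.

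**The case against.** The strongest reply has several parts, and much of it stands.

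- **The definition governs.** The items say an event may be considered in a category. The definition of *related* is inclusive, and an event meeting two *related* items can hardly have a connection ruled out with certainty. A careful investigator would choose *related*. This stands, but it does not stop another investigator relying on the item count.
- **Timing of the judgement.** Adverse events are asked about before dosing at visits 2 to 13, and serious events must be reported within 24 hours. Many events are therefore judged before the next injection, when the item cannot apply. This stands and narrows the point to events judged or revised later.
- **Meaning of study drug.** Section 3.10.1 equates the term with TEV-48125. Even so, the investigator cannot tell whether a single injection was active.
- **The placebo visit is not drug-free.** About 65% of the drug may remain. The argument is therefore strongest for events tied to peak exposure or to the active injection itself.

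Stronger conclusions that a reader might draw are not supported. The three mirrored items do not by themselves let an event meet both lists, since they always split 3–0 or 2–1; overlap needs the non-recurrence or the dechallenge item. The 12 of 32 is not a share of events: it weights hypothetical patterns equally, and half of it needs a dechallenge that a 45-day half-life makes hard to observe. Nor does section 7.1.2 let monitoring stop on a checklist result; it runs "until a determination of a cause unrelated to the study drug or study procedure is made", which means that a cause has been determined.

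**Conclusion.** The point holds in a limited form. Non-recurrence is scored without any condition that active drug was given, and the schedule makes this matter in one arm only. For events with no known pattern, judged after the next injection, *not related* becomes available when timing fits and no other cause is present. Related events of that kind may be understated in the quarterly arm relative to the monthly arms.

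The size cannot be given. The documents contain no event rates by causality pattern, and the pattern counts show eligibility, not frequency. The conclusion assumes that some investigators apply the item count literally and score the item after an injection that may be placebo.

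A reader might infer that related-event rates are not comparable between arms, or that the primary safety assessment is compromised. The documents do not support that. The endpoint is the occurrence of adverse events, and the all-causality, serious and discontinuation summaries do not use the causality call. A missing relationship is counted as related, injection-site findings are summarised separately by active and placebo injection (SAP 7.4), and no inferential comparison is planned. What is exposed is the related-event summary by arm and the causality step in expedited reporting.

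**What to change.** Add to protocol 7.1.4, and repeat in the CRF completion guidance, that the re-administration item is left unscored unless the repeated injection is known to have contained active drug. This works without breaking the blind: by Table 4, every arm receives at least one active injection at visits 5, 8 and 11, so the item can still be scored after those visits.

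For clarity, add that an event meeting both lists is recorded as *reasonable possibility*. This largely restates the existing definition and agrees with the rule that a missing relationship counts as related. It would also settle all 6 patterns that the non-recurrence item makes eligible for *not related*.

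The cost is two sentences and a line of guidance. The downside is that slightly more events will be classed as related. No dose, visit or analysis changes.

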7.1.5. Serious Adverse Events

7.1.5.1. Definition of a Serious Adverse Event

A serious adverse event is an adverse event occurring at any dose that results in any of the following outcomes or actions:

- death
- a life-threatening adverse event (ie, the patient was at immediate risk of death from the event as it occurred); does not include an event that, had it occurred in a more severe form, might have caused death
- inpatient hospitalization or prolongation of existing hospitalization, which means that hospital inpatient admission and/or prolongation of hospital stay were required for treatment of an adverse event, or that they occurred as a consequence of the event. Hospitalizations scheduled prior to study entry will not be considered serious adverse events, unless there was worsening of the pre-existing condition during the patient's participation in this study.
- persistent or significant disability or incapacity (refers to a substantial disruption of one's ability to conduct normal life functions)
- a congenital anomaly/birth defect
- an important medical event that may not result in death, be life-threatening, or require hospitalization, but may jeopardize the patient and may require medical intervention to prevent one of the outcomes listed in this definition. Examples of such events are intensive treatment in an emergency room or at home for allergic bronchospasm, blood dyscrasias or convulsions that do not result in hospitalization, or the development of drug dependency or drug abuse. Note: Any suspected transmission of an infectious agent via a medicinal product is considered an important medical event.

An adverse event that does not meet any of the criteria for seriousness listed above will be regarded as a nonserious adverse event.

7.1.5.2. Expectedness

A serious adverse event that is not included in the Adverse Reaction section of the relevant reference safety information by its specificity, severity, outcome, or frequency is considered an unexpected adverse event. The reference safety information for this study is the Investigator's Brochure.

The sponsor's Pharmacovigilance Department will determine the expectedness for all serious adverse events.

For the purpose of SUSAR reporting, the version of the reference safety information document at the moment of the occurrence of the SUSAR applies.

7.1.5.3. Reporting a Serious Adverse Event

7.1.5.3.1. Investigator Responsibility

To satisfy regulatory requirements, all serious adverse events (as described in Section 7.1.5.1) that occur during the defined study period (including the protocol-defined follow-up period, described in Section 7.1.2), regardless of judged relationship to treatment with the study drug, must be reported to the sponsor by the investigator. The event must be reported within 24 hours of when the investigator learns about it. Completing the serious adverse event form and reporting the event must not be delayed, even if not all the information is available. The investigator does not need to actively monitor patients for adverse events once this study has ended. Serious adverse events occurring in a patient after the defined study period should be reported to the sponsor if the investigator becomes aware of them.

The serious adverse event form should be sent to the local safety officer (LSO) or other designated personnel (a contract research organization [CRO] in a country without a sponsor LSO; contact information is in the Clinical Study Personnel Contact Information section); the LSO will forward the report to the sponsor's Global Patient Safety & Pharmacovigilance Department.

The following information should be provided to record the event accurately and completely:

- study number
- investigator and investigational center identification
- patient number
- onset date and detailed description of adverse event
- investigator's assessment of the relationship of the adverse event to the study drug (no reasonable possibility, reasonable possibility)

Additional information may include the following:

- age and sex of patient
- date of 1st dose of study drug
- date and amount of last administered dose of study drug
- action taken
- outcome, if known
- severity
- explanation of assessment of relatedness
- concomitant therapy (including doses, routes, and regimens) and treatment of the event
- pertinent laboratory or other diagnostic test data
- medical history
- results of dechallenge/rechallenge, if known

- for an adverse event resulting in death:
 - cause of death (whether or not the death is related to study drug)
 - autopsy findings (if available)

Each report of a serious adverse event will be reviewed and evaluated by the investigator and the sponsor to assess the nature of the event and the relationship of the event to the study drug, study procedures, and underlying disease.

Additional information (follow-up) about any serious adverse event unavailable at the initial reporting should be forwarded by the investigational center within 24 hours of when it becomes known to the same address as the initial report.

For all countries, the sponsor's Global Patient Safety & Pharmacovigilance Department will distribute the Council for International Organizations of Medical Sciences form/extensible markup language file to the LSO and/or CRO for local submission to the regulatory authorities, IEC/IRBs, and investigators, according to regulations. The investigator is responsible for ensuring that the IRB/IEC is also informed of the event, in accordance with local regulations.

Blinding will be maintained for the people who are involved directly in the study. Therefore, in case of a SUSAR, only the LSO and/or CRO personnel involved with safety regulatory submissions will receive the unblinded report for regulatory submission; the others will receive a blinded report.

Note: Although pregnancy is not a serious adverse event, the process for reporting a pregnancy is the same as that for reporting a serious adverse event, but using the pregnancy form (see Section 7.2).

